## 2. OBJECTIVES AND ENDPOINTS

**Table 1: Study Objectives and Endpoints**

Primary Objectives	Primary Endpoints
To evaluate the long-term safety and tolerability of AL002 in participants with AD	
 
● Incidence of AEs, including AESIs and SAEs
 
● Vital signs, clinical laboratory results, and incidence of findings from physical, neurological, ophthalmological examinations, and ECG
 
● C-SSRS
 
● MRI abnormalities
 

To evaluate the effect of dose titration on ARIA	
 
● Incidence and severity of ARIA in participants undergoing titration
 

Secondary Objective	Secondary Endpoints
To evaluate the PK of AL002 in participants with AD	
 
● Serum PK concentrations of AL002 and relevant PK parameters
 

To evaluate the effects of AL002 on COAs in participants with AD	
 
● CDR®-SB
 
● MMSE
 
● RBANS-Update
 
● ADAS-Cog13
 
● ADCS-ADL-MCI
 
● ADCOMS
 

Exploratory Objectives	Exploratory Endpoints
To evaluate the effects of AL002 on biomarkers in participants with AD	
 
● Levels of sTREM2 in CSF and/or plasma
 
● Levels of biomarkers related to microglia function in CSF and/or plasma (eg, CSF1R, IL1RN, osteopontin, YKL 40)
 
● Levels of biomarkers related to AD pathology in CSF and/or plasma (eg, Aβ40, Aβ42, pTau, tTau)
 
● Levels of neurodegeneration biomarkers in plasma and/or CSF eg, NfL
 
● Brain volume, assessed by volumetric MRI
 
● Brain pathological tau burden as assessed by longitudinal Tau PET for participants who agree to participate in the optional assessment only
 
● Brain amyloid burden as assessed by longitudinal Amyloid PET scanning for participants who agree to participate in the optional assessment only
 

To evaluate immunogenicity of AL002 in participants with AD	
 
● Incidence of ADAs
 

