### 3. INVESTIGATIONAL PLAN

#### 3.1. Study Design

This is a Phase 2, parallel-group, long-term extension (LTE), dose-blind, global multicenter study to evaluate the long-term safety and efficacy of AL002 in participants with AD. The study will enroll participants who completed the planned treatment period in AL002-2 (parent study). Study sites are located in North America, Australia, Europe, and Argentina.

Participants who were randomized to active treatment in the parent study will remain on their previously assigned dose. Participants who were previously on placebo in the parent study will be assigned to the Titration Cohort, which will initiate with a starting dose of ■ mg/kg with the potential of escalating to ■■ mg/kg per the Titration Algorithm described in [Section 5.1](#).

The primary objectives of this Phase 2-LTE study are to evaluate the long-term safety and tolerability of AL002 at 3 possible doses (ie, 15 mg/kg, 40 mg/kg, and 60 mg/kg) and to assess the effect of a slower dose titration on the incidence and severity of ARIA (see Study Objectives/Endpoints [Table 1](#)).

The secondary objectives include the evaluation of the PK of AL002 as well as clinical outcome assessments (COAs) in participants with AD. A battery of COAs ([Section 14.2](#)) will be administered as secondary assessments over the course of the study. Efficacy assessments will be made during the pre-specified time points throughout the 49-week treatment period and at an end of study (EOS)/Week 57 or early termination (ET) Visit if needed ([Table 9](#)).

The exploratory objectives of this AL002-LTE study are to evaluate biomarkers, and the immunogenicity of AL002 in participants with AD. Exploratory fluid (blood/plasma and CSF), imaging (MRI, Tau positron emission tomography (PET) with the tau radiotracer fluorine-18 MK-6240 ( $[^{18}\text{F}]$ MK-6240) and Amyloid PET) biomarker measures will be assessed. Optional biomarker assessments include: CSF collection, Tau PET and Amyloid PET imaging.

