**Table 2: Titration Algorithm 1 (Starting Dose: ■ mg/kg)**

Week	■	■	■	■
AL002 Dose	■ mg/kg	■ mg/kg	■ mg/kg	■ mg/kg

The evaluation of dosing and its relationship to safety and ARIA within the Titration Cohort will occur only with the unblinded pharmacist, the unblinded pharmacy monitor, the unblinded clinical research organization (CRO) staff, and unblinded safety management team at Alector. ARIA monitoring and management will be consistent with the procedures outlined in the parent study. Additional information about ARIA safety monitoring is described in Section 7.6.4 and Section 7.11.

If emerging data suggests that Titration Algorithm 1 is not effectively reducing the incidence or severity of ARIA, a lower starting dose of ■ mg/kg may be considered. In the event that a decision is made to lower the starting dose, all subsequent participants previously randomized to placebo in the parent study AL002-2 entering this AL002-LTE study will be treated with an initial starting dose of ■ mg/kg and will be administered AL002 every 4 weeks by IV infusion using an up-titration algorithm to reach the target dose of ■ mg/kg per Titration Algorithm 2 (Table 3). The dose escalation includes:

- ■ doses of ■ mg/kg: ■ on ■ and ■ on ■
- ■ doses of ■ mg/kg: ■ on ■ and ■ on ■,
- ■ doses of ■ mg/kg: ■ on ■ and ■ on ■,
- ■ doses of ■ mg/kg: ■ on ■ and ■ on ■
- ■ doses of ■ mg/kg begin on ■, and this dose continues through the final dosing visit.

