| To evaluate the effect of dose titration on ARIA in participants with AD | 
Part 3: Primary Endpoints:
 
 • Incidence and severity of ARIA in participants undergoing titration 
Primary Estimand for Incidence and Severity of ARIA:
 
The estimand for incidence and severity is defined with similar attributes as for the Part 1 primary estimand except that it is applied to incidence and severity of ARIA, and difference in incidence of ARIA events between slower and faster titration groups will be reported
 |
| Secondary Objective | Secondary Endpoints |
| To evaluate the PK of AL002 in participants with early AD | 
 • Serum PK concentrations of AL002 and relevant PK parameters. |
| To evaluate the effects of AL002 with COAs in participants with AD | 
LTE Efficacy Endpoints:
 
 • Disease progression as measured by the CFB in CDR-SB score. • CFB in MMSE score. • CFB in RBANS score. • CFB in ADAS-Cog13 score. • CFB in ADCS-ADL-MCI score. • CFB in ADCOMS. • CFB in modified iADRS. 
Main Estimand for Efficacy:
 
The main estimand for the LTE Efficacy endpoints is defined with similar attributes as for the primary safety estimand in Part 1 except the following.
 
 • Accounting for intercurrent events: a composite strategy will be used to handle intercurrent events as below: 
 ○ Hypothetical strategy for handling premature study drug discontinuation for any reason (data will be considered missing after early discontinuation of study drug plus 37 days). ○ Treatment policy strategy for handling all other intercurrent events. • Population-level summary: the percent reduction relative to placebo decline (the proportional treatment effect), comparing each dose level to placebo. |

| Primary Objectives | Primary Safety Endpoints and Primary Estimand |
|--|--|
| Exploratory Objectives | Exploratory Endpoints |

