3.4 Hypothesis Testing

There are two hypotheses to be tested. First there is the efficacy null hypothesis of the core study: The null and alternate hypotheses for comparing each of the treatment groups to placebo are as follows:

H_0 (null): $\theta \leq 0$, indicating that treatment does not slow disease progression relative to placebo control,

H_1 (alternative): $\theta > 0$, indicating that treatment slows disease progression relative to placebo control,

where θ represents the treatment effect, defined as a proportional reduction of the placebo group clinical decline in the CDR-SB.

Secondly, there is a test of the null hypothesis that dose titration speed has no effect on occurrence of first ARIA events. The null and alternate hypotheses for comparing treatment with slower titration against treatment with faster titration are:

H_0 (null): $\tau = 0$, indicating that slower titration does not change first ARIA event incidence relative to treatment with faster titration,

H_1 (alternative): $\tau \neq 0$, indicating that slower titration changes first ARIA event incidence relative to treatment with faster titration,

where τ represents the slower titration effect, defined as difference in first ARIA event incidence relative to the group with faster titration.

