7.4.8 Magnetic Resonance Imaging (MRI) for ARIA-E and ARIA-H Events

Incidence of the occurrence of ARIA-E within each post-baseline visit will be summarized by radiographic severity for each visit (refer to [Table 7-12](#) and [Table 7-13](#) for analysis visit window definitions) and overall. The same incidence table will be summarized for ARIA-H. In addition to radiographic severity for ARIA-H, individual radiographic severity for microhemorrhages, leptomeningeal hemosiderosis, and macrohemorrhages for the occurrence of ARIA-H will also be summarized by visit and overall.

In the case of multiple values in the baseline analysis visit window, the rules described in the Section [7.1.3.2](#) still apply. In the case of multiple values in a post-baseline analysis visit window, the rules described in the Section [7.1.3.2](#) do not apply to this summary, but the worst-case scenario will be applied as below:

- A participant having a record indicating no ARIA-E and a different record indicating ARIA-E is considered experienced ARIA-E per visit or overall.
- A participant having experienced ARIA-E more than once per visit or overall is counted once in the number of participants with ARIA-E per visit or overall.
- The maximum severity is selected if ARIA-E was observed more than once for a participant per visit or overall post-baseline.

The same rules described above also apply to ARIA-H. In addition, the maximum severity of ARIA-H is selected for a participant per visit or overall post-baseline, and the individual radiographic severity corresponding to the selected ARIA-H will be summarized per visit or overall post-baseline.

APOE genotype, time to the first occurrence, resolution, time to resolution, and reoccurrence will be summarized for participants with ARIA-E. APOE genotype and time to the first occurrence will be summarized for participants with post-baseline ARIA-H.

The number and percentage of participants who had post-baseline ARIA-E but did not have ARIA-H any time post-baseline will be summarized. The number and percentage of participants who had ARIA-H but did not have ARIA-E any time post-baseline will be summarized. Similarly, the number and percentage of participants who had ARIA-H and ARIA-E any time post-baseline will be summarized.

Overall incidence of the occurrence of ARIA-E and ARIA-H will also be summarized by APOE genotype.

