All of the MRI summaries described above will also be provided separately for participants with the following APOE genotype(s) (1) e4 carriers (including e2/e4, e3/e4 and e4/e4), and (2) non-e4 carriers (excluding e2/e4, e3/e4 and e4/e4).

For Integrated Analysis, all summaries described in this section will be provided for events across two studies as defined in Section 7.4.1.2. For LTE Analysis, only the overall summary of ARIA will be provided for events during the LTE Study.

For Integrated Analysis, the difference in proportion of participants with ARIA-E events between a slower titration rate over 48 weeks and a faster titration rate over 48 weeks will be estimated by the Cochran-Mantel-Haenszel (CMH) method adjusting for the APOE e4 status. The faster titration rate will be represented by data from the AL002 60 mg/kg treatment group during the first 48 weeks of the Core Study among participants who were on dose titration (i.e., received the first dose on or after July 22, 2021 in the Core Study) and had at least one evaluable post-baseline MRI scan. The slower titration rate will be represented by data from the first 48 weeks of the LTE Study, among Titration Cohort participants who had at least one evaluable post-baseline MRI scan in the LTE Study. Both 90% and 95% CIs for the difference in the ARIA-E events and p-value will be reported from the CMH method. The same analysis will be repeated for ARIA-H.

The statistical tests (the CMH method) of ARIA events between the slower and faster titration groups will not be performed at the first IA at the time of unblinding of the Core Study due to limited data from the LTE study at this IA, but will be performed in all analyses after the first IA.

In the Integrated Analysis, the Kaplan-Meier curves for the time to the first occurrence of ARIA-E during both the Core and LTE Studies will be plotted. For participants who experienced at least one ARIA-E, the time to the first occurrence of ARIA-E is the time from the first dose date to the onset date of the first ARIA-E occurrence. For participants who did not experience ARIA-E, the censor date will be the earlier date of the last MRI scan date, any death date, and the last dose date plus 90 days. Similarly, the Kaplan-Meier curves for the time to the first occurrence of ARIA-H will be plotted.

All MRI findings will be listed.

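### ARIA severity is half of the primary titration endpoint, but the SAP gives it no like-for-like comparison of slow with fast titration

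*SAP*

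**What the plan says.** Protocol Table 1 and SAP Table 2-1 (Part 3) give the same primary titration endpoint: "Incidence and severity of ARIA in participants undergoing titration". Protocol 3.1 states the aim as "to assess the effect of a slower dose titration on the incidence and severity of ARIA".

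The Part 3 estimand in SAP Table 2-1 takes over the Part 1 attributes for both incidence and severity. It then adds that the "difference in incidence of ARIA events between slower and faster titration groups will be reported". The Part 1 attributes include descriptive summaries by treatment group covering comparable lengths of time. In SAP 3.4 the tested parameter is "defined as difference in first ARIA event incidence relative to the group with faster titration".

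SAP 7.4.8 specifies one comparison of slow with fast titration: a CMH estimate, adjusted for APOE e4 status, of "the difference in proportion of participants with ARIA-E events between a slower titration rate over 48 weeks" and a faster rate over the same span. It is repeated for ARIA-H. The fast group is the 60 mg/kg group in its first 48 Core weeks, "among participants who were on dose titration (i.e., received the first dose on or after July 22, 2021 in the Core Study"), with an evaluable follow-up MRI. The slow group is the Titration Cohort in its first 48 LTE weeks, under the same MRI condition.

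Severity appears earlier in the same section: "Incidence of the occurrence of ARIA-E within each post-baseline visit will be summarized by radiographic severity for each visit" and overall, with the worst grade taken when a participant has several. In the Integrated Analysis these tables use all Core and LTE data by dose group (SAP 7.4.1.2), and the dose group is set by highest dose received (SAP 5.1, 5.2.1).

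**The concern.** The SAP builds a careful matched population for the titration question and then uses it only for whether ARIA occurred. The other half of the endpoint is left to tables that lack the titration-date limit, the 48-week limit and the evaluable-MRI condition.

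Two things are at stake. First, if slower titration made ARIA milder without making it rarer, the planned comparison would estimate no difference and no matched severity estimate would stand beside it. Second, a reader who wants the severity answer will compare the 60 mg/kg and Titration Cohort columns of the general tables. Those columns differ in how treatment was started and in how long participants were watched.

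**Working it through.** **1. The two displays side by side**

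| | CMH comparison (SAP 7.4.8) | Integrated severity tables (SAP 7.4.8, 7.4.1.2) |
|---|---|---|
| Outcome | any-grade ARIA-E; any-grade ARIA-H | radiographic grade, worst value |
| 60 mg/kg group | first dosed on or after 22 July 2021 | everyone grouped by highest dose received |
| Period | first 48 weeks | all Core and LTE data |
| MRI condition | evaluable follow-up scan required | none stated |
| e4 adjustment | yes | no; separate tables by carrier status |

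The LTE-only ARIA summary does not help. Its 60 mg/kg participants are already in long-term treatment, so it contains no fast-titration group.

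**2. Follow-up in the overall row.** The last MRI target day is 1093 in SAP Table 7-12 and 393 in Table 7-13.
- (1093 − 1)/7 = 156 weeks; (393 − 1)/7 = 56 weeks.
- 156/56 = 2.79, about 2.8-fold. Against the 48-week CMH window the factors are 156/48 = 3.25 and 56/48 = 1.17.
- This is a ceiling. It holds for participants who complete both studies. Core dosing is up to 96 weeks (Protocol 1.2.2), and the set includes Core participants who never entered the LTE.

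**3. By-visit rows.** Scheduled MRI visits through Week 48 are 2, 4, 6, 8, 12, 24 and 48 (Core) and 8, 16, 24, 32 and 40 (LTE). Only Weeks 8 and 24 coincide, and their windows differ in days: [51, 71] against [2, 85], and [128, 253] against [142, 197]. The footnote to Table 7-12 says LTE visits are not mapped to Core visits for ARIA results.

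**4. AE tables.** SAP 7.4.3 splits AE summaries, including those by severity, at 48 weeks, which partly matches follow-up. They use AE grade, not radiographic grade, and keep every 60 mg/kg participant. SAP 7.4.1.2.1 applies the split to endpoints selected in Section 8, and Section 8.1.3 names TEAE summaries there, not the ARIA MRI tables.

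**5. How far the overall row could mislead (assumed inputs).** The documents give neither the number of untitrated 60 mg/kg participants nor any severity rates. Assume a true moderate-or-worse rate of 10% in both titrated groups, a fraction f of the comparator untitrated with rate r, and a proportion L of those still event-free who have a late event. Then

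c = (1 − f) × 0.10 + f × r, and table rate = c + (1 − c) × L.

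- f = 0, L = 0: 10.0%, spurious difference 0.
- f = 0.2, r = 0.20, L = 0.03: c = 0.12; 0.12 + 0.88 × 0.03 = 0.146; difference 4.6 points.
- f = 0.3, r = 0.30, L = 0.05: c = 0.16; 0.16 + 0.84 × 0.05 = 0.202; difference 10.2 points.

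The range is 0 to about 10 points. It assumes that untitrated participants fare no better than titrated ones.

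**6. What a matched severity estimate would look like (assumed inputs).** The plan's enrolment figure reproduces: 220 × 0.80 = 176 and 220 × 0.90 = 198. An even split over four groups gives 176/4 = 44 to 198/4 = 49.5; take 44 to 50 per group. The rates, group sizes and power in Protocol 8.1 are blacked out and cannot be reproduced.
- Suppose any ARIA-E is 20% in both groups and moderate-or-worse is 12% fast against 4% slow. The planned estimate is 20 − 20 = 0 points; the severity difference is 12 − 4 = 8 points.
- Unadjusted standard error: √[(0.12 × 0.88 + 0.04 × 0.96)/n] = √(0.144/n), which is 0.0572 at n = 44 and 0.0537 at n = 50. The 95% half-widths are 11.2 and 10.5 points.
- For any ARIA-E of 30% against 15%, with 30% to 50% of events moderate or worse, power at two-sided 0.05 is about 39% to 43% for any grade and 13% to 22% for moderate-or-worse. A matched severity contrast is an estimate, not a test.

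**The case against.** The strongest reply is that severity already has a stated analysis. The Part 3 estimand applies the Part 1 attributes to severity, and the Part 1 summary is descriptive by group. The endpoint concerns severity in those being titrated, and SAP 7.4.8 delivers it for ARIA-E, ARIA-H and each ARIA-H component. The comparative parameter is incidence throughout: Protocol 8.1 and 8.3.3 and SAP 3.4 all agree. This stands, so the gap lies between objective and analysis, not between protocol and SAP. It does not remove the gap, because Protocol 3.1 asks for the effect of slower titration on severity, and the inherited attribute calls for comparable periods.

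Several stronger readings are tempting and are not supported:
- *Severity is ignored, or is radiographic only.* It is tabulated by visit and overall, and AE-grade tables exist. Radiographic grading is the protocol's own ARIA scale (Protocol Table 7).
- *The tables make slow titration look milder whatever the truth.* For a given participant, a longer period can only keep or raise the worst grade. But Protocol 1.4 describes ARIA in anti-amyloid trials as mostly early, so late scans may add little. The existence of untitrated participants is itself inferred from the CMH restriction, and their number is not given.
- *Follow-up is 2.8 times longer.* That is a maximum, for the overall row only.
- *A shift to milder ARIA would be reported as no titration effect.* The parameter is labelled as first-event incidence, and the severity tables would appear beside it.
- *The switch rule in Protocol 5.1 requires this analysis.* "If emerging data suggests that Titration Algorithm 1 is not effectively reducing the incidence or severity of ARIA" governs an in-study decision, not the CMH analysis.

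**Conclusion.** The point holds as a gap in the analysis: the severity half of the primary titration endpoint has no like-for-like comparison of slow with fast titration, although the SAP already defines the population for one. This rests on document text alone.

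The size of any distortion in the existing tables does not. The ceiling on unequal follow-up is 2.8-fold, for completers of both studies in the overall row. The possible spurious advantage for slow titration, 0 to about 10 points, depends wholly on assumed rates and an assumed untitrated share. The tables may favour slow titration; the documents do not show that they must, or by how much.

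This is a cheap improvement that should be made, not a fault in the planned incidence test.

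**What to change.** In SAP 7.4.8, use exactly the two groups, the 48-week window and the evaluable-MRI population of the CMH analysis. Add, for ARIA-E and for ARIA-H:

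1. the distribution of worst radiographic severity, including none;
2. a descriptive e4-adjusted difference with 95% CI in the proportion at or above one threshold on the Protocol Table 7 scale, for example moderate or worse.

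Fix the threshold before the comparison is first run; SAP 7.4.8 already defers the CMH analysis past the first interim. State what it means for each component, because Table 7 rates any leptomeningeal hemosiderosis as at least moderate and any macrohemorrhage as severe. Label the result as estimation, with no further hypothesis test.

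A tabulation of symptomatic ARIA on the same population, from the AE records linked to each ARIA entry (Protocol 7.11), is optional. The primary estimand in SAP Table 2-1 need not take on new quantities.

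The cost is a short SAP addition and about one table from data already collected. The downside is small counts and wide intervals.

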3. STUDY DESIGN

3.1 Study Design

This is a Phase 2, LTE study of participants with AD. The study will enroll participants who completed the planned treatment period in AL002-2 (Core Study). Study sites are located in North America, Australia, Europe, and Argentina.

Participants who were randomized to active treatment in the Core Study will remain on their previously assigned dose. Participants who were previously on placebo in the Core Study will be assigned to the Titration Cohort (TC), which will initiate with a starting dose of either 2 mg/kg or 6 mg/kg that will be increased over 32 weeks or 24 weeks, respectively, to reach the target dose of 60 mg/kg per the Titration Algorithm (for details of the Titration Algorithm, refer to the Study Protocol).

The planned duration of the LTE study is 56 weeks, and LTE study treatment extends from LTE Day 1 to Week 48. Dosing duration may be extended beyond this time through a protocol amendment, within the context of emerging favorable safety data. AL002 will be administered via IV infusion at the study site on Day 1 (after all necessary baseline assessments have been completed) and will be repeated subsequently once every 4 weeks throughout the treatment period.

The first dose of the AL002-LTE should be within the 4-week window (± 5 days) of the last dose of the Core Study, to maintain continuity of study treatment. Delays of the first AL002-LTE dose beyond that window will constitute protocol deviations.

Dosing for any individual participant may be stopped, paused, or reduced based on emerging safety data and/or the development of ARIA-E or ARIA-H. If a participant discontinues the study prior to the end of their planned treatment period, they will need to return for an Early Termination (ET) Visit and that will mark the end of their participation in the study.

At study entry and throughout the treatment period, safety will be assessed through monitoring of AEs (including AESIs and SAEs), changes in laboratory and vital sign values, incidence of findings from physical, neurological, ECG, MRI, ophthalmological exams, and reports of suicidal ideation or behavior. Serum PK will be assessed for investigation of exposure-response and exposure-safety relationships. Blood samples for assessment of ADA will be taken throughout the study.

The COAs, PK assessments, and biomarker assessments (fluid collection and imaging) will be performed prior to dosing and at specific time points during the treatment period and at End of Study (EoS)/ET if needed.

